4.2 Treatment Regimen

The clinical trial is designed as a multi-center, single, randomized dosing, double-blind study with 5 treatment visits, each visit start time separated by at least 48 hours (6 half-lives of CVL-562). We aim to complete all in-person visits for each participant over approximately a 1-2 month period, with likely variation given patient availability and schedule. Below is a more detailed description of procedures.

4.2.1 Clinical Protocol Schedule of Events Completed by an Individual

• Pre-screening - Potential participants will be contacted by phone by a research staff member to determine whether a participant is eligible to participate in an in-person screening visit (baseline visit). The data indicating that a participant is found to be eligible for Visit 1 will be entered directly into a REDCap database. Those who fail to meet eligibility criteria on the phone screen will not be invited to the in-person screening/baseline visit and will not participate in any additional research procedures. Potential participants will then be invited for the baseline visit (in-person assessment) with a doctoral-level clinician or an appropriately trained senior research assistant. Given the longitudinal

nature of the study, as well as planning for attrition, we aim to recruit a total of 120 participants who would be eligible to receive CVL-562 based on medical and psychiatric assessments. Of those, we aim to have 100 participants complete full procedures (we have estimated attrition of 20 participants). The number of participants who are consented may exceed 120 subjects as we anticipate that some will be found ineligible on the first baseline visit due to medical or psychiatric or other reasons.

- Visit 1 This visit will serve as a baseline pre-randomization visit (4-8 hours total, possibly spread across a few days). During this visit, we will obtain informed consent and ascertain full eligibility criteria. The baseline visit will involve a structured clinical interview (SCID-V), Penn Reading Assessment (PRA), Edinburgh Handedness Inventory, spatial working memory task, practice flashing checkerboard task, PANSS, PennCNB letter n-back task, Calgary Depression Scale for Schizophrenia, Beck Anxiety Inventory, Columbia-Suicide Severity Rating Scale—baseline/screening (C-SSRS, toxicology/pregnancy, baseline/screening). urine baseline bloodwork (complete blood count with differential, comprehensive metabolic panel, Hepatitis B, Hepatitis C, HIV; optional genetics), EKG, vital signs, health history, physical exam, MRI eligibility, and an optional mock scanner experience. Pre-existing health information may be used to determine eligibility if it was obtained within 3 weeks prior to the date of consent. All subjects will be tested for COVID-19 as part of Visit 1. COVID-19 testing may be repeated after Visit 1 based on symptoms. All participants will be consented to participate in these procedures, however, only those who are found eligible for test visits will continue with the study. Given the numerous assessments and the length of time to complete them, the practical difficulties in securing MRI scan time, patient availability, and the need to keep patients engaged during the study to minimize dropout, this first visit may be split into a few days within the window of consent and Visit 2 (8 weeks). Following the end of Visit 1, the clinical lead investigator at each site will assess and confirm eligibility for further study visits based on information gathered at that visit and inclusion/exclusion criteria. For those participants for whom eligibility is difficult to determine, they will be discussed with a larger group of investigators to reach consensus on eligibility. Following determination of eligibility for test visits, participants will be randomized to a dosing schedule as follows: placebo, 1 mg, 4 mg, 15 mg, or 25 mg —75% of the patients will be randomized to get the highest dose on the last visit.
- Visit 2 Test visit (4-6 hours): Initial clinical assessments including urine sample for toxicology/pregnancy exam, PANSS, vital signs, Columbia-Suicide Severity Rating Scale—since last visit (C-SSRS, since last visit), MRI safety assessment. A lifestyle questionnaire will be administered to understand basic events that occurred in the hours before the scan, including how much caffeine was used, how much food was eaten, pain levels and whether nicotine was used. If participants have not had a meal within 2 hours prior to

the start of the study visit, they will be offered a small meal to induce a fed state, as the effects of the study drug have a different timing during a fed vs. fasting state. A brief refresher session on the spatial working memory task and the flashing checkerboard task will be presented to the participants to remind them of the task instructions, at this point or after drug administration prior to the start of scanning. Following this, the treatment visit medication will be administered. Then, the subject will have vital signs re-checked after medication administration, and enter the fMRI scanner to complete approximately 90 minutes (up to 2 hours) of data collection. Data collected in the scanner includes both high-resolution T1-weighted and T2-weighted structural images (approximately 20 minutes), 4 multi-band functional BOLD runs that involve trials of spatial working memory, trials of motor control, and trials of spatial working memory with distraction (approximately 40 minutes total), resting state scan (approximately 10 minutes), a resting state arterial spin labeling (ASL) scan to assess for changes in cerebral blood flow (approximately 10 minutes), and brief visual checkboard stimuli (to explore neurovascular coupling effects of CVL-562; approximately 5 min). The first test visit will also include a diffusion-weighted image (DWI) (approximately 20 minutes). If the DWI is not collected at the first test visit it will be collected on one of the subsequent test visits. Plasma levels of CVL-562 will be obtained prior to and following imaging with a blood draw from either venipuncture or an IV continued with a slow rate of normal saline infused during the scan (20 mL/hour) to minimize needlesticks. The slow rate of normal saline is used to keep the IV open during the scan, and prevent clotting in the IV. The use of either two venipunctures (one prior to imaging and one following imaging) or a continuous IV will be made after assessing patient preference, and procedure feasibility. Vital signs, PANSS, Columbia-Suicide Severity Rating Scale since last visit (C-SSRS, since last visit), and PennCNB battery will be administered immediately after the completion of the scan. A study physician will be available for the entire test visit. Subjects will be observed for at least 2 hours following dose administration, and provided follow-up. Visits 3, 4, 5, 6 will be identical to Visit 2, with at least 48 hours of separation (six half-lives of CVL-562) between the start of each test visit day. All participants will be contacted by phone approximately 24 hours after the visit to briefly assess for any adverse effects. COVID-19 testing may be done if symptoms are suspected.

- Visits 3, 4, 5, 6 all identical to Visit 2.
- Visit 7 Follow up visit (approximately 2 hours): Individual follow up and debriefing. At this time female participants will receive a final urine pregnancy test. All participants will have a final blood draw for labwork for safety monitoring (complete blood count (CBC) with differential, and complete metabolic profile (CMP)). All participants will be called approximately 1 month after this follow up visit to assess for long-term effects

4.3 Special Procedures Related to COVID-19

Given the ongoing pandemic, and the shifting waves of illness that have ensued since this protocol was approved, there will be additional precautions to ensure the safety of the participant and the staff during the course of the study and pandemic. All sites will follow their required site procedures for cleaning, distancing and testing. During Visit 1, all participants will receive COVID-19 testing. If a participant tests positive, they will be removed from study procedures and asked to follow current CDC guidelines for isolation and further testing. If, after the isolation period, they do not develop symptoms, they will be evaluated for continuation in the study. If they become symptomatic, the severity of their illness will be evaluated for potential exclusion from the study. As the exclusion criterion includes unstable medical illnesses, those participants who are COVID-19 positive and have significant symptoms may be excluded under this criterion. Should symptoms develop during the course of the study, participants will be tested for COVID-19. The severity of their symptoms, in conjunction with the outcome of testing, will be assessed for possible exclusion from the study, as determined by the clinical lead investigator at each site. Those who recover from their symptoms and are willing to resume study procedures must be free of significant symptoms at the time of restarting study procedures. Those who test positive for COVID-19 during this study will be designated as such for purposes of exploratory data analyses.

Study procedures will generally continue to be on-site; however, to minimize contact, some assessments for Visit 1 may be conducted or monitored virtually, at the discretion of the site PI and research staff and based on the needs of the participant and local site. These assessments may include clinical interviews, scales, questionnaires, and the PRA. The sWM and Flashing Checkerboard task practices and medical assessments will continue to be done in-person. For the virtual components, study participants will be instructed to participate virtually in the same way they would while onsite (ex: alone in a room, no distractions, available for the designated amount of time).

All virtual assessments will be conducted using secure, password-protected, HIPAA-compliant videoconferencing platform. Conducting these assessments virtually will allow research staff to continue research, maintain social distance, and also observe necessary components of affect (facial expression, vocal quality) that would be difficult to do behind masks. Finally, to ensure that assessment scoring can be reliable, we will record interviews, which may be an optional part of the study. Recording will allow investigators to ensure reliability and accuracy of data collection while conducting assessments virtually. Consenting for recording of assessments will be optional for participation in the study. All recordings will be stored centrally at Yale using a secure, password-protected HIPAA-compliant platform and each site will keep a copy of their recordings in a secure, password-protected HIPAA-compliant platform. Only trained research staff members and investigators will have access to these videos for the purposes of assessing the reliability and accuracy of these assessments. Study processes may continue to

be modified in response to the COVID-19 pandemic, as medical and public health considerations evolve.

4.4 Randomization

Patients will each have 5 treatment visits, and the order of placebo, 1 mg, 4 mg, 15 mg or 25 mg dosing will be randomized through the Investigational Drug Services at Yale New Haven Hospital. Drug dosing schedules will be balanced within and across sites. Each treatment visit start time would be separated by >=48 hours (6 half-lives of CVL-562). The randomization will assign 75% of patients to the highest dose on the last visit and 25% will receive the highest dose on one of the other four visits. Only the highest dose will be subject to this pseudorandomization strategy, and all other doses will be randomly distributed. This randomization strategy is intended to minimize the impact on study completion of the association of the 25 mg dose with nausea in approximately 30% of subjects, which might unblind subjects and lead to study discontinuation. Patients and investigators will be blind to the randomization. Cerevel will distribute the drug to the Yale Pharmacy directly. Yale Pharmacy will then distribute the drug in kits determined in the randomization protocol.

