3.1 Primary Endpoint

To test if CVL-562 has dose-related effects in schizophrenia patients on putative neural biomarkers of D1R/D5R stimulation. We will examine the dose-specific effects of CVL-562 on blood oxygen level dependent (BOLD) signal change during working memory procedures. The primary outcome measure is an analysis of variance of the dose-dependent effects of CVL-562 on the blood oxygen level dependent signal (BOLD) during spatial working memory. Post-hoc univariate tests will quantify directional dose-related CVL-562 effects.

3.2 Secondary Endpoint 1

To test in how many participants CVL-562 produces a dose-related modulation of BOLD signal during working memory procedures.

3.3 Secondary Endpoint 2

To test if CVL-562 produces a dose-related modulation of sWM behavioral performance collected during fMRI. This will be examined using the behavioral data generated during neuroimaging to quantify dose-related CVL-562 effects on sWM performance both with and without distractors.

3.4 Secondary Endpoint 3

We plan to directly examine the association between trial-by-trial sWM performance and task-evoked BOLD signal by regressing trial-by-trial sWM performance with and without distractors with the relevant BOLD signal.

3.5 Secondary Endpoint 4

We will examine the dose-dependent effects of CVL-562 on the functional connectivity of brain regions during spatial working memory.

3.6 Secondary Endpoint 5

We will examine the dose-dependent effects of CVL-562 on the resting state functional connectivity using a data-driven global brain connectivity (GBC) metric.

3.7 Secondary Endpoint 6

We will compare the change in resting state GBC as a function of CVL-562 dose with the transcriptomic maps from the Allen Human Brain Atlas relevant to risk genes in schizophrenia.

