All preprocessing of imaging data will follow Human Connectome Project (HCP) pipelines(67). For each CIFTI-based gray-ordinate, least-squares coefficients will be generated independently reflecting BOLD signal during task conditions. We will use a general linear model to fit the hemodynamic response function (HRF) using a finite impulse response function (FIR) for the timepoints covering the encoding (timepoints 1-2) and delay epochs (timepoints 3-14) and the natural decay in the HRF (timepoints 15-20). Assessing the HRF across these 20 timepoints for each task condition (motor, spatial working memory, distractionnear and distraction-far) will allow us to examine the effects of dose response across our epochs of interest. From these general linear models, we will form within-subject contrasts for second-level analyses. We will use non-parametric combination (NPC) to examine the multivariate effects of dose (5 levels) and task condition (motor, spatial working memory, distraction-near and distraction-far) at each timepoint within each voxel of an independently defined mask of spatial working memory regions from the prior work of [name] (co-investigator). When compared with an ANOVA or related MANOVA, NPC provides a more statistically efficient and robust approach for this primary endpoint, while still allowing for testing of dose-dependent effects of drug on the task BOLD signal at different timepoints(68). NPC has the additional advantage of accommodating the multivariate and potentially non-normally distributed nature of our endpoints. Furthermore, NPC maintains better power at fixed sample sizes than traditional multivariate tests, which have increasing power as the number of modalities increases, until an inflection point, after which traditional test power declines. Significant voxels will be determined using non-parametric statistics and corrections for multiple comparisons as appropriate.

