We will test if CVL-562 produces a dose-related modulation of sWM performance. We will leverage behavioral data generated during neuroimaging to quantify dose-related CVL-562 effects on sWM performance and also on sWM performance with distraction. Here, the outcome measure will be the sWM performance measured as the angular difference between the target presentation and the participant's response. We will conduct a 4 (task condition--motor, spatial working memory, near-distraction, far-distraction) x 5 (dose) repeated measures ANOVA. Post-hoc analyses will be conducted to demonstrate the directional effects of behavioral performance with respect to dosing. All statistics will be corrected for multiple

comparisons.

10.1.4 Secondary Endpoint 3

We will directly examine the association between sWM performance and task-evoked BOLD signal. An analysis of variance of the dose-dependent effects of CVL-562 on the task-evoked BOLD signal will be conducted as described for the Primary Endpoint, but instead will use the trial-by-trial regressor of sWM performance as a covariate. sWM performance will be measured as described in Secondary Endpoint 2, and will be treated as a covariate of interest in the above-specified general linear model. An effect of a 5 (drug dose) x 4 (task condition) interaction with the sWM precision covariate would indicate that the drug has an effect of BOLD signal change that is specifically associated with a change in trial-by-trial sWM performance.

10.1.5 Secondary Endpoint 4

We will conduct an analysis of variance of the dose-dependent effects of CVL-562 on the functional connectivity of brain regions during spatial working memory. In contrast to the task-evoked modeling, here we will use 'time point' selection methods to isolate specific time points during the delay period of each trial, which we will combine into a time series. This BOLD signal will be used to co-vary a given region of interest with the rest of the brain. Given prior work by our team we will focus on the fronto-parietal control network (FPCN) as a 'seed' region for this task-evoked FC analysis. Specifically, we will quantify covariation of the extracted FPCN signals with all other CIFTI greyordinates. This index of FPCN 'functional integrity' will be obtained across sWM conditions and CVL-562 doses for each subject and will then be entered into 2nd-level random effect analyses.

10.1.6 Secondary Endpoint 5

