We will conduct an analysis of variance of the dose-dependent effects of CVL-562 on the resting state functional connectivity using a data-driven global brain connectivity (GBC) metric. Notably, GBC examines connectivity from a given voxel (or area) to all other voxels (or areas) simultaneously by computing average connectivity strength—thereby producing an unbiased approach as to the location of dysconnectivity. Also, unlike typical seed approaches, GBC involves one statistical test per voxel (or area) rather than one test per voxel-to-voxel pairing, substantially reducing multiple comparisons. Per-subject GBC will be obtained for each CIFTI greyordinate at each CVL-562 dose for each subject and will then be entered into 2nd-level random effect analyses.

10.1.7 Secondary Endpoint 6

Resulting resting state GBC maps will be compared against transcriptomic maps of genes relevant to psychotic disease processes from the Allen Human Brain

Atlas (https://human.brain-map.org/) using correlation analyses. This will allow us to see whether spatial patterns of resting state GBC map onto regions enriched for gene expression relevant to schizophrenia and related illnesses.

10.1.8 Exploratory Endpoint 1

We will conduct exploratory analyses to test whether genetic variants are related to BOLD signal changes in response to CVL-562. Genetic variants examined may include, but are not limited to, those genes involved in CVL-562 metabolism, the dopamine 1 receptor, or schizophrenia illness development.

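### 25 mg falls on the last test visit in 75% of patients and no Section 10 analysis includes visit, so the dose effects in 10.1.3 and 10.1.6 absorb any average change over the five scans

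*Combined protocol and SAP*

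**What the plan says.** Section 4.4 sets the rule for the top dose: "The randomization will assign 75% of patients to the highest dose on the last visit". For the remaining patients the same section says that "25% will receive the highest dose on one of the other four visits". It does not say how that 25% is divided among the four earlier test visits. The other treatments are placed at random, and the section adds "Drug dosing schedules will be balanced within and across sites".

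Section 2.4 expects randomized order to let practice effects be separated from drug effects. The planned analyses are:

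- **10.1.1 (primary):** "We will use non-parametric combination (NPC) to examine the multivariate effects of dose (5 levels) and task condition", by timepoint and voxel. The timepoints are samples of the hemodynamic response within a trial, not visits. The section also says "we will form within-subject contrasts for second-level analyses", without defining those contrasts.
- **3.1 (primary, follow-up):** "Post-hoc univariate tests will quantify directional dose-related CVL-562 effects".
- **10.1.3 (task performance):** "We will conduct a 4 (task condition--motor, spatial working memory, near-distraction, far-distraction) x 5 (dose) repeated measures ANOVA".
- **10.1.6 (resting-state connectivity):** an "analysis of variance of the dose-dependent effects of CVL-562 on the resting state functional connectivity", with dose as the only factor.

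Covariates are promised in two other places: psychotropic medication (6.2) and urine THC (7.2.3). Visit, period, order or sequence is named nowhere in Section 10.

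**The concern.** In a five-period crossover, dose comparisons are protected from practice, habituation and scanner drift when every dose is spread equally over the periods. The 75% rule deliberately breaks that for 25 mg. Balance within and across sites cannot restore it, because no schedule that obeys the rule gives 25 mg the same mean position as the other treatments. A period term would then do the work, and Section 10 has none.

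What is at stake is the upper end of the dose-response curve. The trial is meant to detect an inverted U, and 25 mg is its top dose. Change over repeated scanning that is attributed to 25 mg could create a downturn or hide one.

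**Working it through.** **The plan's own figure.** The plan gives no figure for visit imbalance. Its nearest number is the detectable effect of 0.18 to 0.37 for N=100 to 25 (10.1.1). A plain two-sided paired t-test at 80% power gives 0.28 and 0.58 instead. The plan's range is for the combined NPC test, and Figure 2 is not available, so this is a separate matter. The single-test value of 0.28 is used below only to price the fix.

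**Step 1: mean test-visit position.** Input: the 75/25 rule in 4.4. Positions 1 to 5 sum to 15, so each other treatment averages (15 − position of 25 mg)/4.

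| Spread of the 25% | 25 mg | Each other treatment | Gap |
|---|---|---|---|
| Even over visits 1-4 (assumed) | 0.75×5 + 0.25×2.5 = 4.375 | 2.656 | 1.72 |
| All at visit 1 | 0.75×5 + 0.25×1 = 4.00 | 2.75 | 1.25 |
| All at visit 4 | 0.75×5 + 0.25×4 = 4.75 | 2.5625 | 2.19 |

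Placebo, 1, 4 and 15 mg share the same expected position, so contrasts among them are not biased on average.

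**Step 2: bias in 25 mg minus placebo, even spread.**

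- Linear drift b per visit: bias = 1.72b. At b=0.10 it is 0.172.
- A single step s after the first scan: 93.75% of 25 mg scans and 76.56% of each other treatment's scans come after it, so bias = 0.172s. At s=0.5 it is 0.086.

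**Step 3: false positives.** Illustration only: one outcome, N=100, no drug effect, nominal 5%. Drift is assumed, in units of the session SD or of the SD of the paired difference. For b=0.10, the position difference between 25 mg and placebo has variance 3.76, which adds 0.01×3.76 = 0.038 to the variance of the paired difference.

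- Session SD: noncentrality = 10×0.172/√2.038 = 1.20, giving 22%.
- Paired SD: noncentrality = 10×0.172/√1.038 = 1.69, giving 38.6% (38% by simulation).
- Over the possible spreads at b=0.10: 14-33% (session SD) and 23-58% (paired SD).
- At b=0.05: 9% and 13%.
- Repeated-measures dose main effect at b=0.10: 19% and 34%.
- Early step of 0.2, 0.3 or 0.5: 6, 6 and 9% (session SD); 5, 8 and 14% (paired SD).
- 15 mg against placebo: 4-6% throughout.
- With categorical visit in the model: 3-6% for the 25 mg and dose tests in every scenario.

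**Step 4: what changes for the primary analysis.** Two features that 10.1.1 leaves open decide the error rate.

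- *Contrast.* Drift common to all task conditions cancels from dose × condition and from memory-minus-motor contrasts (simulated error 4-5%). Drift confined to the memory conditions does not: 18% (session SD) or 35% (paired SD) at b=0.10, with half of the session variance assumed shared across conditions.
- *Permutation.* With an unadjusted statistic and b=0.10, drawing orders uniformly gives 22% (session SD) or 36% (paired SD) for 25 mg against placebo. Drawing them with the actual 75/25 probabilities gives 5% or 4%.

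**Step 5: price of a visit term.** Expected information over the 120 possible orders gives the variance of 25 mg minus placebo relative to no adjustment. Detectable d for one two-sided paired test at N=100 scales as 0.283×√factor.

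| Model | Even spread | All 25% on one visit |
|---|---|---|
| All five sessions jointly, categorical visit | 1.56; d = 0.35 | 1.71; d = 0.37 |
| All five sessions jointly, linear visit | 1.19 | 1.09 to 1.39 |
| Each two-session difference adjusted separately, categorical visit | 2.39; d = 0.44 | 4.76; d = 0.62 |

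In the joint models, contrasts among the other treatments keep a factor of 1.00.

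**The case against.** The strongest reply is that the plan already knows about practice effects. Section 2.4 says they can be separated, participants are trained at Visit 1 (7.2.1), and each scan is preceded by a refresher (4.1). Learning may be largely over before the first scan, and Step 3 shows that an early step does little harm. All of that stands as a limit on size. It does not supply a method: 2.4 states an aim that Section 10 does not carry out.

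A second reply concerns the primary endpoint. A reader might infer that the primary NPC test has an inflated error rate. The documents do not support that, because 10.1.1 fixes neither the second-level contrasts nor the permutation scheme, and some reasonable choices hold the error rate. What stands is narrower. The 25 mg estimate is biased if drift affects the contrast used, and a permutation scheme that holds the error rate does not remove bias from an unadjusted estimate.

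A reader might also infer that any 25 mg effect would be a practice effect, or that the 75/25 allocation should be abandoned. Neither follows. No drift is reported, and because 25% of patients receive 25 mg earlier, dose and visit can be separated at group level. The loss of precision from adjustment is real and should be acknowledged.

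**Conclusion.** The concern holds in a limited form. It is firm for the 10.1.3 repeated-measures ANOVA and the 10.1.6 resting-state analysis: followed as written, their dose main effects and 25 mg contrasts include any average change over the five scans. Resting-state connectivity has no control condition from which drift could cancel. For the primary analysis, bias in the 25 mg estimate and inflated test error are both conditional, as set out above.

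The visit gap of 1.72 rests on an assumed even spread, but no permitted spread takes it below 1.25. The error rates rest on assumed drift in a single outcome and do not model the voxelwise test. They show that modest steady drift would matter, not that it exists.

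Secondary Endpoint 1 (10.1.2) has a separate limit. Each patient has one scan per dose, so dose and visit are fully confounded within the individual. This should be fixed before analysis; it does not call the design into question.

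**What to change.** Leave the allocation unchanged, and record how the 25% is spread over test visits 1-4, since both the bias and the cost depend on it.

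- **10.1.1:** fit the second-level dose analysis jointly to all five sessions per patient, with patient effects, dose and categorical test visit (1-5), and take the dose contrasts from that model. Do not add visit to separate two-session difference scores. If dose order is permuted, draw orders with the actual 75/25 probabilities. Uniform draws do not protect an unadjusted statistic.
- **10.1.3:** use a mixed model with dose, condition, dose × condition, visit and visit × condition.
- **10.1.4 to 10.1.6:** add visit to the dose analyses in the same joint way.
- **10.1.2:** state that no per-patient visit term can be fitted, and that the proportion of responders must be read with that limit.
- State that the term removes average drift only.

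The work is wording and code. The statistical cost falls on 25 mg: with the joint-model factors above, power at d=0.28 drops from 80% to 61% under even spread, or 57% if the 25% falls on one visit. A linear visit term is cheaper (73%) but removes only linear drift. Under a step of 0.5 after the first scan it leaves 25 mg against placebo at 11% (session SD) or 18% (paired SD), no better than no adjustment, so categorical visit is preferable.
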